#### **6.9.9 Discontinuation of Study Therapy after Complete Response**

Discontinuation of treatment may be considered for subjects who have attained a confirmed CR that have been treated for at least 24 weeks with pembrolizumab and had at least two treatments with pembrolizumab beyond the date when the initial CR was declared. Subjects who then experience radiographic disease progression may be eligible for up to one year of additional treatment with pembrolizumab via the Second Course Phase at the discretion of the investigator if no cancer treatment was administered since the last dose of pembrolizumab, the subject meets the safety parameters listed in the Inclusion/Exclusion criteria, and the trial is open. Subjects will resume therapy at the same dose and schedule at the time of initial discontinuation. Additional details are provided in Section 5.6.

CUPem	C/37/2017	Imperial College London	V7.0, 08.12.2021
-------	-----------	----------------------------	------------------

## 7 PHARMACOVIGILANCE

### 7.1 Adverse Event (AE)

An AE is any untoward medical occurrence in a patient or clinical trial subject administered a medicinal product and which does not necessarily have a causal relationship with this treatment. An AE can therefore be any unfavourable and unintended sign (including an abnormal laboratory finding), symptom, or disease temporally associated with the use of the trial medication, whether or not considered related to the IMP.

Any worsening (i.e., any clinically significant adverse change in frequency and/or intensity) of a pre-existing condition that is temporally associated with the study treatment, is also an adverse event.

#### 7.1.1 Disease Progression

Disease progression is a worsening of a patient's condition attributable to the disease for which the study medication is being given. This may be an increase in severity of the disease or increase in the symptoms of the disease. The development of new, or progression of existing metastasis to the primary cancer under study should be considered as disease progression and not an AE. Events that are unequivocally due to disease progression should not be reported as AEs during the study.

### 7.2 Adverse Event recording

AEs will be collected throughout the study, from the point of consent until the Safety Follow Up visit\*; they will be followed up according to local practice until the event has stabilised or resolved, or the follow-up visit, whichever is sooner. Serious Adverse Events (SAEs) will also be recorded throughout the study. See Appendix D for further details.

At the Safety Follow Up visit, any AEs of Grade > 1 which remain unresolved will be followed up by the Investigator until the resolution of the AE to Grade 0-1 or until the beginning of a new anti-neoplastic therapy, whichever occurs first, but without further recording in the eCRF.

\*SAEs, including death that occur within 90 days of the end of treatment or before initiation of a new anti-cancer treatment should also be followed and recorded.

Details to be collected in the eCRF for each AE will include:

- AE description
- Date of onset and date of resolution
- Severity
- Seriousness
- Relationship to study treatment

#### 7.2.1 Severity of Adverse Events

Severity is a measure of intensity; whereas seriousness is defined by the criteria in section 7.4.

Severity will be assessed using the grading scales found in the National Cancer Institute CTCAE version 4.03 (June 2010) for all adverse events with an assigned CTCAE term.

For those events without assigned CTCAE grades, the recommendation on page 1 of the CTCAE that converts mild, moderate and severe into CTCAE grades should be used. A copy of the CTCAE version 4.03 can be downloaded from the Cancer Therapy Evaluation Program website (<http://ctep.cancer.gov>).

CUPem	C/37/2017	Imperial College London	V7.0, 08.12.2021
-------	-----------	----------------------------	------------------

Any adverse event which changes CTCAE grade over the course of a given episode will have each change of grade recorded on the adverse event eCRF.

All adverse events regardless of CTCAE grade must also be evaluated for seriousness.

### 7.2.2 Causality of Adverse Events

The Investigator will assess causal relationship between the study treatment and each AE.

Unrelated:	No evidence of any causal relationship
Unlikely:	There is little evidence to suggest there is a causal relationship (e.g. event did not occur within a reasonable time after administration of the trial medication). There is another reasonable explanation for the event (e.g. the patient's clinical condition, other concomitant treatment).
Possible:	There is some evidence to suggest a causal relationship (e.g. because the event occurs within a reasonable time after administration of the trial medication). However, the influence of other factors may have contributed to the event (e.g. the patient's clinical condition, other concomitant treatments).
Probable:	There is evidence to suggest a causal relationship and the influence of other factors is unlikely.
Definite:	There is clear evidence to suggest a causal relationship and other possible contributing factors can be ruled out.

CUPem	C/37/2017	Imperial College London	V7.0, 08.12.2021
-------	-----------	----------------------------	------------------

### 7.3 Abnormal Laboratory Test Results

All clinically important abnormal laboratory test results occurring during the study will be recorded as adverse events. The clinically important abnormal laboratory tests will be repeated at appropriate intervals until they return either to baseline or to a level deemed acceptable by the investigator and the clinical monitor, or until a diagnosis that explains them is made.

### 7.4 Serious Adverse Events (SAE)

#### 7.4.1 Definition of SAE

An SAE is defined as any event that

- Results in death;
- Is life-threatening\*;
- Requires hospitalisation or prolongation of existing inpatient's hospitalisation\*\*;
- Results in persistent or significant disability or incapacity;
- Is a congenital abnormality or birth defect;
- Is another important medical event (that may not result in death, not be life threatening, or not require hospitalization may be considered a serious adverse event when, based upon appropriate medical judgment, the event may jeopardize the subject and may require medical or surgical intervention to prevent one of the outcomes listed above.

**N.B.** In addition to the above criteria, adverse events meeting either of the below criteria, although not serious per ICH definition, are reportable to MSD in the same timeframe as SAEs to meet certain local requirements. Therefore, these events are considered serious by MSD for collection purposes:

- A new cancer (that is not a condition of the study)
- Is associated with an overdose (whether accidental or intentional).

\* "Life-threatening" in the definition of "serious" refers to an event in which the subject was at risk of death at the time of the event; it does not refer to an event which hypothetically might have caused death if it were more severe.

\*\* "Hospitalisation" means any unexpected admission to a hospital department. It does not usually apply to scheduled admissions that were planned before study inclusion or visits to casualty (without admission).

#### 7.4.2 Reporting of SAEs

Rapid reporting of all SAEs, i.e. within 24 hours of the Principal Investigator or designee becoming aware of the event, occurring during the study must be performed as detailed in the Pharmacovigilance Manual. If the investigator becomes aware of safety information that appears to be drug related, involving a patient who participated in the study, even after an individual patient has completed the study, this should be reported to the Sponsor.

**The SAE should be reported electronically to the study team at the Imperial Clinical Trials Section via the CUPem inform database as detailed in the Pharmacovigilance study manual.**

All SAEs will be reviewed by the Chief Investigator (CI) or a designated medically qualified representative to confirm expectedness and causality. Reporting of SAEs and review by

CUPem	C/37/2017	Imperial College London	V7.0, 08.12.2021
-------	-----------	----------------------------	------------------

the CI will be via the trial data collection system (eCRF) as detailed in the Pharmacovigilance Study Manual.

Following documented assessment by the CI, the completed SAE form will be sent by email to the Sponsor by the study team at the CTS within the pre-specified timelines. Regardless of expectedness or causality, all SAEs must also be reported to MSD by the Sponsor, within 2 working days (to meet certain local requirements).

## **7.5 Definition of a Serious Adverse Reaction (SAR)**

A SAR is defined as a SAE that is judged to be related to any dose of study drug administered to the subject.

## **7.6 Definition of Suspected Unexpected Serious Adverse Reaction (SUSAR)**

Any SAR that is NOT consistent with the applicable product information as set out in the Investigator Brochure (IB) or Summary of Product Characteristics (SmPC).

### **7.6.1 Reporting of SUSARs**

SUSARs should be notified to the appropriate regulatory authority, the relevant REC and the Sponsor in accordance with regulatory requirements. SUSARs which are fatal or life-threatening will be reported not later than seven days after alerting the sponsor to the reaction. Any additional relevant information will be sent within eight days of the report.

A SUSAR which is not fatal or life-threatening will be reported within 15 days.

Follow up of patients who have experienced a SUSAR should continue until recovery is complete or the condition has stabilised.

## **7.7 Development Safety Update Reports (DSURs)**

Development Safety Update Reports (DSURs) will be submitted to the Sponsor, the relevant Ethics Committees and Regulatory Authorities in accordance with regulatory requirements.

## **7.8 Reporting of Pregnancy and Lactation**

Although pregnancy and lactation are not considered adverse events, it is the responsibility of investigators or their designees to report any pregnancy or lactation in a subject (spontaneously reported to them) that occurs during the trial.

Pregnancies and lactations that occur after the consent form is signed but before treatment allocation must be reported by the investigator if they cause the subject to be excluded from the trial, or are the result of a protocol-specified intervention, including but not limited to washout or discontinuation of usual therapy, diet, placebo treatment or a procedure.

Pregnancies and lactations that occur from the time of treatment allocation through 120 days following cessation of Sponsor's product, or 30 days following cessation of treatment if the subject initiates new anticancer therapy, whichever is earlier, must be reported by the investigator. All reported pregnancies must be followed to the completion/termination

CUPem	C/37/2017	Imperial College London	V7.0, 08.12.2021
-------	-----------	----------------------------	------------------

of the pregnancy. Pregnancy outcomes of spontaneous abortion, missed abortion, benign hydatidiform mole, blighted ovum, fetal death, intrauterine death, miscarriage and stillbirth must be reported as serious events (Important Medical Events). If the pregnancy continues to term, the outcome (health of infant) must also be reported.

Such events must be reported within 24 hours to the Sponsor, who will then report to MSD Global Safety within 2 days.

## 7.9 Definition of Overdose and Reporting

For purposes of this trial, an overdose of pembrolizumab will be defined as any dose of 1,000 mg or greater ( $\geq 5$  times the indicated dose). No specific information is available on the treatment of overdose of pembrolizumab. Appropriate supportive treatment should be provided if clinically indicated. In the event of overdose, the subject should be observed closely for signs of toxicity.

If an adverse event(s) is associated with ("results from") the overdose of a MSD product, the adverse event(s) is reported as a serious adverse event, even if no other seriousness criteria are met.

If a dose of MSD's product meeting the protocol definition of overdose is taken without any associated clinical symptoms or abnormal laboratory results, the overdose is reported as a non-serious Event of Clinical Interest (ECI), using the terminology "accidental or intentional overdose without adverse effect."

All reports of overdose with and without an adverse event must be reported within 24 hours to the Sponsor, who will then report it to MSD Global Safety. Within 2 days.

## 7.10 Events of Clinical Interest

Selected non-serious and serious adverse events are also known as Events of Clinical Interest (ECI) and must be reported within 24 hours to the Sponsor and within 2 working days to MSD Global Safety.

For the time period beginning when the consent form is signed until treatment allocation, any ECI, or follow up to an ECI, that occurs to any subject must be reported within 24 hours to the Sponsor and within 2 working days to MSD Global Safety if it causes the subject to be excluded from the trial, or is the result of a protocol-specified intervention, including but not limited to washout or discontinuation of usual therapy, diet, placebo treatment or a procedure.

For the time period beginning at treatment allocation through 90 days following cessation of treatment, or 30 days following cessation of treatment if the subject initiates new anticancer therapy, whichever is earlier, any ECI, or follow up to an ECI, whether or not related to MSD product, must be reported within 24 hours to the Sponsor and within 24 hours to MSD Global Safety.

CUPem	C/37/2017	Imperial College London	V7.0, 08.12.2021
-------	-----------	----------------------------	------------------

**Events of clinical interest for this trial include:**

An overdose of MSD product, as defined in Section 7.2.1 - Definition of an Overdose for This Protocol and Reporting of Overdose to the Sponsor, that is not associated with clinical symptoms or abnormal laboratory results.

An elevated AST or ALT lab value that is greater than or equal to 3X the upper limit of normal and an elevated total bilirubin lab value that is greater than or equal to 2X the upper limit of normal and, at the same time, an alkaline phosphatase lab value that is less than 2X the upper limit of normal, as determined by way of protocol-specified laboratory testing or unscheduled laboratory testing.\*

***\*Note: These criteria are based upon available regulatory guidance documents. The purpose of the criteria is to specify a threshold of abnormal hepatic tests that may require an additional evaluation for an underlying aetiology.***

**7.11 Reporting urgent safety measures**

If any urgent safety measures are taken the CI/Sponsor shall immediately and in any event no later than 3 days from the date the measures are taken, give written notice to the MHRA and the relevant REC of the measures taken and the circumstances giving rise to those measures.

CUPem	C/37/2017	Imperial College London	V7.0, 08.12.2021
-------	-----------	----------------------------	------------------

## 8 STATISTICAL ANALYSES

### 8.1.1 Statistical Analysis Plan

Response rates can be assessed in patients who have completed at least 2 cycles of trial therapy

- Overall response rates by immune-related (irRECIST) & RECIST criteria:
  - Disease Control Rate (DCR), Overall Survival (OS) & Progression Free Survival (PFS).
- Overall response rates by immune-related (irRECIST) & RECIST criteria in a First-line setting
  - DCR, OS & PFS.
- QOL analysis by EORTC-QLQC30.
- Incidence of adverse events up to 8 weeks days after the last dose of Pembrolizumab.
  - incidence of adverse events up to 8 weeks days after the last dose of Pembrolizumab in PS2 patients.
- Exploratory Identification of genomic biomarkers predictive of immune response to Pembrolizumab in CUP patients and correlates of efficacy, toxicity and QOL.
  - Where patients are co-registered and consented to the NHSE 100k genome project – the data from this project will be requested to cross-correlate with this study.

### 8.2 Sample size, power considerations and planned recruitment rate

An interim futility analysis was originally pre-planned after recruiting 24 (out of 57) patients in Cohort 2 and a final analysis after 77 participants completed the study (20 for Cohort 1 and 57 for Cohort 2).  $\geq 1$  documented response in Cohort 1 was achieved in May 2020, enabling Cohort 2 to open and Cohort 1 to close once sufficient evaluable participants had been enrolled. Due to the unexpected challenges recruiting study participants outlined in the Trial Summary and sections 1.3.1 and 3.1, particularly for Cohort 2, Cohort 1 was reopened and expanded. Version 7.0 of the protocol has formally closed Cohort 2 with approval from the TMG, MSD and combined TSC/IDMC. Cohort 1 (pre-treated patients) remains a crucial area of unmet need with no standard of care treatment existing.

The study statistics were originally modelled on the UK CUP-ONE trial based on the primary study end-point of response in cohort 2.

The sample size has thus been recalculated to accommodate the shift of focus to assessing PFS and OS in Cohort 1 and complete removal of Cohort 2. The sample sizes were recalculated based on the Brookmeyer-Crowley test for median survival time (Brookmeyer R and Crowley JJ. A confidence interval for the median survival time. Biometrics. 1982: 38, 29-41).

CUPem	C/37/2017	Imperial College London	V7.0, 08.12.2021
-------	-----------	----------------------------	------------------

Assuming a historic null PFS of 2 months and an alternative PFS of 4 months, the minimum required sample size to determine the median PFS for the study cohort is 46 (at 0.05 level of significance, one-sided, 90% power). For the OS, assuming a null OS of 4 months and an alternative OS of 7 months, the required minimum sample size is 67 with the same level of significance and power. Therefore, the final sample size needed to determine both the median PFS and OS is 67 (the higher sample size). In the event that this sample size will be difficult to recruit within the additional accrual period of 12 months, a sample size of 31 will still be able determine the median PFS and 45 the median OS with a power of 80%.

Power Size	Null Median Survival	Alternative Median Survival	Min Sample Size
0.80	2 months PFS	4 months	31
0.90	2 months	4 months	46
0.80	4 months OS	6 months	83
0.80	4 months	7 months	45
0.90	4 months	6 months	122
0.90	4 months	7 months	67

The study will therefore aim to recruit between 31 and 67 patients to Cohort 1 within the allotted study period. This sample size range is estimated to have a power of 80% to 90% in determining the PFS and/or the OS of the study cohort.

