5.1 Primary Efficacy Endpoint

The overall response to treatment is assessed using RECIST v1.1 and immune-related (irRECIST). Appendices A and B in the protocol present the guidelines for evaluation of objective tumour response Using RECIST 1.1 (Response Evaluation Criteria in Solid Tumours) or immune-related RECIST. The disease control rate will be calculated.

Disease Control Rate (DCR) - is defined as the proportion of patients in whom the best overall response is determined as complete response (CR), partial response (PR) or stable disease (SD) for at least 12 weeks in either RECIST or irRECIST criteria.

Overall Survival (OS) - defined as the length of time from study enrolment until death, withdrawal of consent, last follow-up date if lost to follow-up or the end of the study, whichever occurs first.

Progression Free Survival (PFS) – is defined as the length of time from study enrolment to first evidence of progressive disease identified at follow-up or confirmed disease progression at the end of the trial or death. Patients will be censored at the last follow-up date if they are lost to follow-up, withdrawn from the study or have not progressed at the end of study. Median PFS and its 95% confidence interval will be reported. Kaplan-Meier survival curves will also be plotted.

Quality of Life (QOL) is measured as scores from the EORTC QLQ-C30 version 3 questionnaire which will be administered at baseline, after 3 months and then at discontinuation of study treatment.

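### At the fallback sizes of 31 (PFS) and 45 (OS), the stated 80% power and one-sided 5% level do not hold together; at an exact size of 5% or less, power is about 72%

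*Protocol*

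**What the plan says.** Protocol 8.2 gives the basis of the recalculation: "The sample sizes were recalculated based on the Brookmeyer-Crowley test for median survival time". The level and main power are "at 0.05 level of significance, one-sided, 90% power". The effects are set by "Assuming a historic null PFS of 2 months and an alternative PFS of 4 months" and, for survival, "assuming a null OS of 4 months and an alternative OS of 7 months".

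At 90% power, "the minimum required sample size to determine the median PFS for the study cohort is 46" and "the final sample size needed to determine both the median PFS and OS is 67". If recruitment falls short, "a sample size of 31 will still be able determine the median PFS and 45 the median OS with a power of 80"%. The section closes by claiming 80% to 90% power across the range of 31 to 67. SAP 3.5 repeats all of this.

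Neither document gives a variance form, a transformation or a rejection boundary. On analysis, SAP section 6 sets two-tailed tests at 5%, and SAP 6.3 summarises OS and PFS descriptively. SAP 5.1 adds "Median PFS and its 95% confidence interval will be reported", without naming the type of interval.

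**The concern.** At a fixed time, a median test compares the estimated survival proportion with one half. If the standard error is evaluated at the estimate, it is too small once the estimate is well above one half, so the test rejects too readily in the direction of interest. With 31 or 45 patients there are few possible cut-offs, and moving the cut-off by one patient changes both size and power materially.

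The fallback figures are what the plan relies on if recruitment is slow. If they depend on a cut-off whose real size exceeds 5%, the plan overstates what it can show with 31 or 45 patients.

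**Working it through.** **Inputs.** Medians, level and sample sizes are from Protocol 8.2. Exponential survival and no censoring before the null median are assumptions; the documents state neither.

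Survival at the null time under the alternative is S = 0.5^(null median / alternative median):
- PFS at 2 months: 0.5^(2/4) = 0.707
- OS at 4 months: 0.5^(4/7) = 0.673

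**Test.** Without early censoring, the Kaplan-Meier estimate at the null time is X/N, with X binomial. The success probability is 0.5 under the null and S under the alternative. The untransformed Greenwood form rejects when z = (X/N − 0.5) / √[(X/N)(1 − X/N)/N] is at least 1.645.

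**Reproducing the plan.** With this form, the smallest N with exact power of at least 80% is 31 (PFS 2 vs 4), 45 (OS 4 vs 7) and 83 (OS 4 vs 6). All three 80% rows of the plan's table match. The log-log form gives 35, 51 and 93, and the null-variance form gives 34, 48 and 83. The 90% rows fit less closely: exact power is 90.2% at 46, 88.3% at 67 and 91.5% at 122.

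**Cut-offs.**
- N=31: 20/31 = 0.645, z = 0.145/√(0.645 × 0.355/31) = 1.69, reject. At 19/31, z = 1.29, do not reject.
- N=45: 28/45 = 0.622, z = 0.122/√(0.622 × 0.378/45) = 1.69, reject. At 27/45, z = 1.37, do not reject.

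**Exact size and power.** Size is P(X ≥ cut-off) with probability 0.5; power is the same tail with probability S.

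| N, endpoint | Cut-off | Size | Power |
|---|---|---|---|
| 31, PFS | 20 (untransformed, 1.645) | 7.5% | 83.1% |
| 31, PFS | 21 | 3.5% | 71.9% |
| 45, OS | 28 (untransformed, 1.645) | 6.8% | 81.3% |
| 45, OS | 29 | 3.6% | 71.8% |
| 46, PFS | 29 (untransformed, 1.645) | 5.2% | 90.2% |
| 46, PFS | 30 | 2.7% | 83.7% |
| 67, OS | 41 (untransformed, 1.645) | 4.3% | 88.3% |
| 67, OS | 42 | 2.5% | 82.5% |

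At N=31 and N=45 no whole-patient cut-off gives both a size of at most 5% and 80% power. The first sizes that do are 35 for PFS and 51 for OS.

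**Early censoring.** The documents give no rate. In simulations with 2% to 10% censored before the null time, the untransformed form at N=31 and N=45 has size of about 5.4% to 6.8% and power of about 76% to 80%. At N=67 its size is about 4.8% to 5.4%.

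**Whole range.** Over N=31 to 67 without censoring, the untransformed form has size 4.0% to 7.5% (mean 5.5%) and exceeds 5% at 23 of 37 sizes. The log-log form has size 2.5% to 5.4% and exceeds 5% at 4 of 37 (39, 46, 55 and 64).

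**At the SAP's two-tailed 5%.** With critical value 1.96, the untransformed cut-offs become 21/31, 29/45, 30/46 and 42/67, which are the second line of each pair above. Power is then about 72%, 72%, 84% and 83%. The upper-tail size is 3.5%, 3.6%, 2.7% and 2.5%, against a nominal 2.5%.

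**The case against.** The strongest objection is that the SAP plans no one-sided declaration. SAP section 6 sets two-tailed 5%, SAP 6.3 describes OS and PFS without a test against 2 or 4 months, and the Trial Summary calls the trial hypothesis generating. This stands. A reader might infer that OS or PFS could be declared above the null too easily; the documents do not support that. At 1.96 the upper tail stays below 5% at all four planned sizes.

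The variance form is also inferred. Matching three table rows is good evidence for it, but not proof. The shortfall in power does not depend on the inference, because under the stated assumptions any cut-off on the count of event-free patients with size at most 5% gives about 72%.

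Much of the excess is discreteness: even the null-variance form exceeds 5% at 16 of the 37 sizes, and N=31 is the worst of them for the untransformed form. Light censoring smooths this.

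The PFS figures are idealised as well. The first scan is at 12 weeks (Protocol 5.9.15), after the 2-month null, so event-free status at 2 months would reflect only deaths and progression found clinically. The 7.5% is a property of the planning calculation, not a forecast of the trial's PFS error rate.

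**Conclusion.** The point holds for the two fallback sizes. As planned, 80% power at N=31 and N=45 goes with an exact one-sided size of 7.5% and 6.8%; holding the size at 5% or less leaves about 72%. This rests on exponential survival and no early censoring. With 2% to 10% censoring the gap narrows on size, but power under the untransformed form also slips to about 76% to 80%.

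Two wider readings are not supported. The test does not fail its level throughout the plan: without early censoring, N=67 is within 5% and N=46 is over by 0.2 percentage points. Nor do the documents say that the trial is likely to end near 31 or 45; they give a range and a closing date, with no accrual forecast.

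The plan's sizes can be reproduced, so this is not a slip in arithmetic. It is a stated level and a stated power that do not hold together, in a plan that leaves the test unspecified.

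**What to change.** 1. In Protocol 8.2 (including its closing claim of 80% to 90% power) and SAP 3.5, restate power at one-sided 5% as about 72% for PFS at N=31 and about 72% for OS at N=45. Give OS at N=67 as about 88%. For PFS at N=46, give 90% with its size of 5.2%.
2. In SAP 6.3, name the form of the median test and of the interval, and use the same form for both. Log-log is one option. It stays closer to 5% but does not guarantee it, and it shares the 5.2% at N=46.
3. Reconcile the one-sided 5% used for planning with the two-tailed 5% in SAP section 6 and the descriptive analysis in SAP 6.3, and say whether any comparison with 2 or 4 months will be made. If two-tailed 5% is kept, restate power at that level: with the untransformed form, about 72% at N=31 and N=45, 84% at N=46 and 83% at N=67. Another form would need its own figures.

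The cost is a few restated figures and a short addition to the SAP. The target of 67 need not change. The downside is less favourable stated power at the fallback sizes.
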